## 4. Study procedures

### **Burden**

The burden placed on participants has been minimised as much as possible by carefully considering the inclusion of each measure in the cross-sectional study and reducing the number of memories recalled in the cross-sectional and intervention parts of the study. Furthermore, the sessions can be split into several shorter sessions should this ease the burden on the participant. Breaks will be offered at regular intervals in each testing session and the researcher will monitor the participant carefully to ensure they are not experiencing a large burden during the study.

### **Risk of Distress**

Both Part 1 and Part 2 of the study have been designed to minimise the chance of the participant experiencing distress during the study. Recalling memories can be distressing and thus the focus of this study, in line with the literature, is on positive memories with the participant only asked to recall one negative memory and three positive memories over the course of the study.

Should the participant become distressed at any point then the study will be terminated and the researcher will discuss this with them. The supervisors of this project have extensive clinical experience in this group and will be available for consultation should this situation arise. In addition, the researcher has experience working with this group of people and will manage the situation should it arise with the support of the supervisors. Any clinically relevant events will be discussed with the individuals' care team with the participant's permission to enable them to follow up on this at a later date.

### **Recruitment**

People with a diagnosis of non-affective psychosis aged 18 - 65yrs will be recruited from local community mental health teams and inpatient wards within South London and Maudsley NHS Trust. Further eligibility criteria for the study are a score of at least 18 on the experiential subscale of the Clinical Assessment Interview for Negative Symptoms to ensure at least a moderate level of current negative symptomatology. These individuals will be identified by clinicians in their care team who will introduce the study to them and ask if they are happy for the researcher to contact them. They will be provided with the written information sheets and the opportunity to discuss with others and consider the information for at least 24 hours. The researcher will then get in touch to discuss they would like to take part. Informed consent will then be obtained from all the participants.

### **Measures**

#### **Part 1 Cross-sectional Study**

##### **Autobiographical Memory Specificity Task (Painter & Kring, 2016)**

This task will be used in the cross-sectional study (part 1) and then adapted for use in the intervention study (part 2).

Participants will be asked to generate a narrative for an event that occurred in the past at a specific time and place and did not last longer than one day. They will be asked to do this for 2 separate events, one positive and one negative. The participants will complete one practice trial where they will be asked to generate a narrative for a time when "they listened to music or the radio". The participant will be given feedback on this practice trial (e.g. "Exactly, now do the same for the rest of the narratives", or "Good, but for the rest of the task please tell me about an event that occurred at a specific time or place") and

then begin the memory task. For each cue the participant will be prompted as follows: "Picture a specific time in the past when a [positive or negative] event occurred. Tell me about it in as much detail as possible, as if you were telling a story."

The participants will then complete a questionnaire relating to the memory to assess how detailed they found the experience and how positive/negative they found the memory to be.

Two independent coders will rate the emotional valence, temporal referencing (references to the past/future) and flexibility (specificity and generalisability) of the narratives produced.

#### **Verbal Fluency Test (Lezak 2012)**

This will be used as a brief assessment of verbal fluency which may be a potential confounder for memory recall.

#### **Letter-Number Sequencing (Wechsler, 2011)**

This will be used as a brief assessment of working memory which again may be a potential confounder for memory recall.

#### **Clinical Assessment Interview for Negative Symptoms (CAINS) (Horan, Kring et al. 2011)**

This is an interviewer-administered assessment for negative symptoms in schizophrenia. Each item is scored from 0 (no impairment) – 4 (severe deficit). There are nine items in the experiential subscale including motivation, recent consummatory pleasure (last week) and anticipatory pleasure (next week) reported by the individual for social, recreational, work/school activities and relationships with family and friends. The expressive subscale includes four items assessing facial expressions, gestures, quantity and quality of speech.

#### **Scale for the Assessment of Positive Symptoms (Andreasen 1984)**

This 34-item scale will be used as a measure of the levels of positive symptomatology currently being experienced by the individual, each item is rated from 0 (absent) to 5 (severe). The items are grouped into four subscales assessing delusional beliefs, hallucinations, bizarre behaviour and thought disorder.

#### **Time use Survey (Fowler, Hodgekins et al. 2009)**

This is a measure of functioning which assesses how much time an individual spends in different activities including household chores, paid work, voluntary work, leisure activities, childcare, sport and hobbies. The number of hours spent in each of these domains is summarized as Constructive Economic Activity (CEA) and Structured Activity (SA).

#### **Beck Depression Inventory (BDI-II) (Beck, Steer et al. 1996)**

This 21-item self-report scale, rated on a 4-point scale from 0 – 3 (total score ranges from 0 to 63, >13 indicates a clinically-relevant level of depression) will be used to assess the levels of depressive symptoms currently experienced by the individual.

#### **Dysfunctional Attitudes Scale (Weissman and Beck 1978)**

This 40-item scale will be included as an assessment of self-defeatist beliefs. Each item consists of a statement and a 7-point Likert scale (1 = fully disagree, 7 = fully agree). The total score ranges from 40-280 and the higher the score the more dysfunctional attitudes that person has endorsed.

### **Part 2 Experimental Study**

## **Outcomes**

The participants will be asked to rate the following items before and after their participation in either the intervention or control condition. These are rated on 100-point visual analogue scales from 1 “Not at All” to 10 “Very Much So”. These are similar to those used in experience sampling studies where these repeated measures have been shown to be reliable and valid (Gard, Kring et al. 2007, Oorschot, Lataster et al. 2011, Gard, Sanchez et al. 2014).

- 1) Right now I feel [enthusiastic, satisfied, relaxed, cheerful]
- 2) Right now I feel [down, guilty, anxious, annoyed]
- 3) How likely the event is to happen again.
- 4) How able they would feel to engage in the future event.
- 5) How enjoyable the future event would be.

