## Study Synopsis

[figure not shown]
Full Title	Is there a Relationship between Memory for Past Events and Motivation for Future Activities?
Short Title/Acronym	The Relationship between Autobiographical Memory and Motivation
Protocol Version number and Date	V4 14/11/16
Study Duration	27 months
Study Design	A cross-sectional, experimental study with a pilot intervention study component.
Sponsor/Co-sponsors	South London and Maudsley NHS Trust
Chief Investigator	[name]
REC number	
Primary objective	Cross sectional associations between autobiographical episodic memory, motivation, experience of pleasure and depression will be examined.
Secondary objective (s)	An intervention study will be conducted to further explore the potential causal role of autobiographical episodic memory in experiential negative symptoms. This will use a brief intervention targeting memory flexibility which is hypothesised to improve pleasure and motivation outcomes.
Number of Subjects	35-40
Main Inclusion Criteria	A diagnosis of non-affective psychosis (as determined by medical records). Aged 18-65yrs. A score of at least 18 on the Clinical Assessment Interview for Negative Symptoms. A good command of the English language.
Statistical Methodology and Analysis	Correlational analyses will be conducted to examine the relationships hypothesised in Part 1 of the study. The ratings provided before and after the study will be analysed in a between-groups ANOVA to assess the effect of the brief intervention on mood, motivation, anticipatory pleasure and self-efficacy beliefs.

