### **Control Condition**

Participants will complete the same task as above but without any of the intervention prompts. They will also be asked to generate a narrative for two positive events that they think may happen again in the future.

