### **Procedure**

Part 1: Participants will complete the baseline autobiographical memory task which involves recalling 1 positive and 1 negative event which will be audio-recorded and coded by two independent raters. Then participants will complete the two subtests of the Wechsler Abbreviated Intelligence Scale - verbal fluency and letter-number sequencing which assess working memory. Two questionnaires that assess depression symptoms and negative thinking (Beck Depression Inventory and Dysfunctional Attitudes Scale) will then be completed by the participant. Finally, three interviews assessing symptoms and functioning will be conducted by the researcher (CAINS, Time Use Survey and Scale for the Assessment of Positive Symptoms (SAPS). This session should last approximately 1.5-2hrs.

Part 2: After Part 1 the participants will be randomized to the intervention or control group using a 2:1 ratio and the “sealed envelope” online software. This will be done by the Chief Investigator who will record the randomisation process and outcome. At the start of the Part 2 session the participants will be asked to select a positive event to describe. They will then complete the visual analogue scales assessing positive and negative feelings, motivation, anticipatory pleasure and self-efficacy. The participants will then complete either the intervention or control task before repeating the visual analogue scales again. The intervention and control task both involve describing this positive event; the control task with no prompts and the intervention task with prompts and videos encouraging them to include more detail in their recall and to link it to past and future events as well. Participants will do this process for two positive events and this session should last approximately 1 hr. Participants will be asked to complete a brief feedback questionnaire at the end of their participation in the study.

This concludes the participant’s involvement in the research.

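### Part 2 names motivation as an outcome, but none of its five ratings asks about it directly; by elimination it rests on how likely the event is to recur

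*Combined protocol and SAP*

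**What the plan says.** The Synopsis describes Part 2 as a "brief intervention targeting memory flexibility which is hypothesised to improve pleasure and motivation outcomes", and its analysis paragraph lists motivation among the outcomes to be compared between groups. The Introduction also names motivation as an outcome of the intervention study. The Procedure section says that participants complete "visual analogue scales assessing positive and negative feelings, motivation, anticipatory pleasure and self-efficacy" before and after the task.

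The Outcomes section under Part 2 lists five ratings. The first two are sets of current-mood adjectives, positive and negative. The other three concern the event:

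- item 3: "How likely the event is to happen again"
- item 4: "How able they would feel to engage in the future event"
- item 5: "How enjoyable the future event would be"

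The section does not say which item measures which construct.

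Events are selected in the same way in both arms. Control participants "generate a narrative for two positive events that they think may happen again in the future", and the Intervention Condition section has the equivalent instruction. According to the Procedure section, the event is chosen first and the baseline ratings follow.

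Part 1 carries the primary objective: "Cross sectional associations between autobiographical episodic memory, motivation, experience of pleasure and depression will be examined". There, motivation is covered by the experiential subscale of the CAINS.

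**The concern.** The plan promises a motivation result from Part 2, but no item is recognisably a motivation item. If item 3 takes that role, the analysis will report a change in expected recurrence as a change in motivation. The two can diverge both ways. A routine or externally arranged event is likely to recur whether or not the person wants it. A wanted activity may be rated unlikely because of money, access or other people. A positive finding on item 3 would therefore not establish a motivation effect, and a null finding would not rule one out.

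There is a second, weaker worry. Item 3 comes close to repeating the criterion by which events are selected, and it is rated after selection. Low values may be uncommon at baseline, leaving less room for improvement.

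**Working it through.** **Step 1. Match constructs to items.** The Procedure section names five constructs and the Outcomes section lists five ratings. By content:

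| Construct (Procedure) | Rating (Outcomes) | Basis |
|---|---|---|
| Positive feelings | Item 1 | current positive mood adjectives |
| Negative feelings | Item 2 | current negative mood adjectives |
| Self-efficacy | Item 4 | perceived ability to take part |
| Anticipatory pleasure | Item 5 | expected enjoyment |
| Motivation | Item 3 | the only item left |

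The adjective *enthusiastic* in item 1 does not fill the gap. It is one of four mood words about the present moment and is not tied to the activity.

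**Step 2. Look for another source of motivation data after the task.** The CAINS covers motivation but is given in the Part 1 session, and randomisation follows Part 1. The Procedure section schedules no repeat. The intervention includes a prompt asking whether the person would do the activity again, but this is part of the treatment in one arm and is not a rated outcome. Item 3 is therefore the only candidate for a before-and-after comparison between arms.

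**Step 3. Could item 3 be near its maximum at baseline?** The documents give no mean, SD or proportion at the maximum, so this is an illustration on assumed values. Take a normal rating with SD σ = 20 and a true gain of 10 points, capped at 100. The mean of a capped normal variable is

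M(μ) = μ·Φ(a) − σ·φ(a) + 100·[1 − Φ(a)], with a = (100 − μ)/σ,

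and the observed gain is M(μ + 10) − M(μ).

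| Assumed baseline mean | M(μ) | M(μ + 10) | Observed gain | Loss | At maximum at baseline |
|---|---|---|---|---|---|
| 50 | 49.96 | 59.83 | 9.87 | 1% | 0.6% |
| 60 | 59.83 | 69.41 | 9.58 | 4% | 2% |
| 80 | 78.33 | 86.04 | 7.71 | 23% | 16% |
| 90 | 86.04 | 92.02 | 5.98 | 40% | 31% |

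**Step 4. Effect on power under further assumptions.** A simulation used 24 versus 12 participants, a t-test on change scores at two-sided 0.05, SD 20, a before–after correlation of 0.6 and a true gain of 18 points. Uncapped power is about 79%. With the cap at 100 it is:

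| Assumed baseline mean | 50 | 60 | 70 | 80 | 90 |
|---|---|---|---|---|---|
| Power | 78% | 77% | 72% | 63% | 50% |

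Under these assumptions a ceiling costs little below a baseline mean of about 70 and a good deal above it.

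**Step 5. What the plan's own figures add.** The plan has no figure for this item to reproduce. Its sample-size statements concern a correlation and a detectable effect for the group comparison, and neither bears on what item 3 measures. The Outcomes section also describes a 100-point scale whose anchors run from 1 to 10. That must be reconciled before a maximum can be defined; the figures above take 100 as the top.

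**The case against.** The strongest reply is that motivation is measured where the trial's main question is asked. The title, "Is there a Relationship between Memory for Past Events and Motivation for Future Activities", corresponds to the Part 1 objective, and the CAINS serves it. This stands. A reader might infer from the Part 2 gap that the title question goes unmeasured; the documents do not support that. The gap is confined to one outcome of a secondary pilot component.

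Second, the mapping is inferred. The Outcomes section assigns no constructs, and items 3 to 5 are written in indirect speech, so the wording on the form may differ. This stands as a limit on certainty. But no other listed item is a better candidate, and the missing map is itself something to correct.

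Third, for a self-chosen activity, rated likelihood of recurrence may be a fair proxy for intention. That is arguable, but the plan does not make the case, and the item refers to the event happening rather than to the person choosing to do it. The Outcomes section cites experience-sampling studies in support of similar scales; whether they support this item cannot be judged from the documents.

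Fourth, a reader might infer that item 3 is bound to start near its maximum. The documents do not show this. Thinking that an event may recur is a weak criterion, and entry requires at least 18 on the CAINS experiential subscale, which could plausibly lower such ratings. Because both arms select events in the same way, the selection would not in itself bias the comparison. The risk is loss of sensitivity.

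**Conclusion.** The point holds for Part 2 only. Motivation is a stated outcome there, none of the five ratings asks about it directly, and the item left by elimination measures expected recurrence. This conclusion rests on matching items to constructs by content and on the wording given in the Outcomes section; it needs no assumed numbers. The CAINS protects the Part 1 question but cannot show an intervention effect.

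The ceiling is a possibility to check, not a finding. The illustrated loss of 1% to 40% depends entirely on an assumed baseline mean between 50 and 90 and an SD of 20.

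The change is worth making before data collection, because a motivation rating that was never taken cannot be recovered afterwards.

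**What to change.** 1. Add one direct rating, for example *How motivated do you feel to do this again?*, given before and after the task in both arms, and name it as the Part 2 motivation outcome.
2. State in the Outcomes section which construct each item measures. Keep item 3 as a separately labelled expectancy item.
3. Inspect the baseline distribution of item 3, including the proportion at the maximum, before interpreting its change. Reconcile the 100-point scale with its 1-to-10 anchors so that the maximum is defined.

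The cost is one more line on the form. With two events rated before and after, that is 2 × 2 = 4 extra ratings per participant, each taking seconds, plus a minor amendment. The downside is one more item to complete and report.

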## **Intervention**

This is based on the memory task described previously, which will enable the specificity, affect and temporal references in the narratives generated during the intervention to be compared to those generated in the baseline task.

### **Intervention Condition**

In contrast to the baseline task participants will be asked to generate narratives for positive events they think may happen again in the future.

The autobiographical memory task described previously will also be adapted to include the following intervention components:

- 1) An animated video with people explaining how they find memory helpful in deciding what they do and don't want to do in the future, and how this is motivating.
- 2) Cues provided during the generation of the narrative as follows:
  - a. Why did you choose this activity? Did this activity give you a sense of achievement? How enjoyable was it?
  - b. Where is it/ When is it/Who is there?
  - c. Sight/Hear/Smell/Sound/Taste.
- 3) A reminder of the link between memory and anticipation
  - a. Would you do this activity again? Why/why not?
- 4) A reminder of the links between this memory/event and others.
  - a. Can you link this to other events?
  - b. What does this memory tell us about you as a person?

### **Control Condition**

Participants will complete the same task as above but without any of the intervention prompts. They will also be asked to generate a narrative for two positive events that they think may happen again in the future.

### **Feedback Questionnaire**

Participants will be asked to complete a brief feedback questionnaire regarding their experience of the intervention and what elements of it were helpful. The questionnaire will include a free text box for participants to provide general feedback on their experience.

### **Procedure**

Part 1: Participants will complete the baseline autobiographical memory task which involves recalling 1 positive and 1 negative event which will be audio-recorded and coded by two independent raters. Then participants will complete the two subtests of the Wechsler Abbreviated Intelligence Scale - verbal fluency and letter-number sequencing which assess working memory. Two questionnaires that assess depression symptoms and negative thinking (Beck Depression Inventory and Dysfunctional Attitudes Scale) will then be completed by the participant. Finally, three interviews assessing symptoms and functioning will be conducted by the researcher (CAINS, Time Use Survey and Scale for the Assessment of Positive Symptoms (SAPS). This session should last approximately 1.5-2hrs.

Part 2: After Part 1 the participants will be randomized to the intervention or control group using a 2:1 ratio and the “sealed envelope” online software. This will be done by the Chief Investigator who will record the randomisation process and outcome. At the start of the Part 2 session the participants will be asked to select a positive event to describe. They will then complete the visual analogue scales assessing positive and negative feelings, motivation, anticipatory pleasure and self-efficacy. The participants will then complete either the intervention or control task before repeating the visual analogue scales again. The intervention and control task both involve describing this positive event; the control task with no prompts and the intervention task with prompts and videos encouraging them to include more detail in their recall and to link it to past and future events as well. Participants will do this process for two positive events and this session should last approximately 1 hr. Participants will be asked to complete a brief feedback questionnaire at the end of their participation in the study.

This concludes the participant’s involvement in the research.

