## **3. Sample Size, Statistics, Selection and Withdrawal of Subjects**

People with a diagnosis of non-affective psychosis aged 18 - 65yrs will be recruited from local community mental health teams and inpatient wards within South London and Maudsley NHS Trust. Further eligibility criteria for the study are a score of at least 18 on the experiential subscale of the Clinical Assessment Interview for Negative Symptoms to ensure at least a moderate level of current negative symptomatology.

A power analysis conducted in GPower Software (version 3.2) with power at 0.8 and  $\alpha = 0.05$  found a sample size of 32 would be sufficient to replicate a correlation with a medium effect size of 0.43 between memory specificity and negative symptoms reported by Harrison and Fowler (2004). To account for drop-outs a sample size of 35-40 will be recruited, if there are few drop-outs this will also increase the power of the study. This sample size with a randomisation ratio of 2:1 is sufficient to detect an F statistic of 0.43 with power at 0.8 and 0.53 with power at 0.9.

There will be three recruitment routes in the study;

1. If recruited through a clinical team then the participant will first be approached by a member of their care team to introduce the study. If they indicate that they are happy to consider the project and give verbal consent for the researcher to contact them then they will be provided with the information sheet. The researcher will then contact them again after at least 24 hours to discuss their potential participation.
2. If recruited through CRIS then potential participants will first be approached by the researcher. This will be done by phone or letter, depending on the preference indicated by the potential participant.
3. If recruited through a recruitment poster then the participant will contact the researcher using the details provided on the poster.

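### Does giving the CAINS interview only at the end of Part 1 leave the entry score of 18 unconfirmed?

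*Combined protocol and SAP*

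**What the plan says.** The Combined protocol and SAP sets the entry score in section 3 and again under Recruitment in section 4: "a score of at least 18 on the experiential subscale of the Clinical Assessment Interview for Negative Symptoms". The Study Synopsis gives the same cut-off without naming a subscale.

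Recruitment in section 4 describes the care-team route: "These individuals will be identified by clinicians in their care team who will introduce the study to them". Section 3 adds two more routes: "If recruited through CRIS then potential participants will first be approached by the researcher", and "If recruited through a recruitment poster then the participant will contact the researcher using the details provided on the poster". No route includes a CAINS rating. Access to Medical Records (section 6) covers checking the diagnosis and recording participation, not obtaining a CAINS score.

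Under Procedure, Part 1 opens with the memory task (one positive and one negative event), followed by the cognitive tests and two questionnaires. The interviews come last: "Finally, three interviews assessing symptoms and functioning will be conducted by the researcher (CAINS, Time Use Survey". Part 2 then begins: "After Part 1 the participants will be randomized to the intervention or control group using a 2:1 ratio".

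On numbers, section 3 states that "a sample size of 32 would be sufficient" for the target correlation, and "To account for drop-outs a sample size of 35-40 will be recruited".

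**The concern.** An entry criterion is normally confirmed before study procedures start. Here the criterion depends on an interviewer-rated scale, and the only rating described comes after the recall. Risk of Distress in section 4 accepts that recall can be upsetting and limits the whole study to one negative memory. On the written order, someone who later scores below 18 has already done that recall. The safeguards in section 4 (breaks, monitoring, stopping if distressed, supervisor and care-team follow-up) act during or after the recall and cannot spare that person.

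The protocol also has no sentence on what happens below 18, whether those Part 1 data are analysed, or whether such people count towards the 35 to 40. If they did count, they would use up the margin over 32 that is meant for drop-outs. Finally, a cut-off of 18 on an unnamed CAINS score, as in the synopsis, could be read as the whole scale, which would admit different people.

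**Working it through.** **Order of events, from Recruitment and Procedure in section 4**

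1. Identification, information and consent: no CAINS described.
2. Part 1 memory task: one positive and one negative recall.
3. Verbal fluency, letter-number sequencing, BDI-II, Dysfunctional Attitudes Scale.
4. Interviews, including the CAINS.
5. Randomisation 2:1.
6. Part 2 session.

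Step 4 follows step 2, so the score is not shown to be known before recall. Step 4 precedes step 5, so it is known before allocation. Anyone excluded for a score below 18 at that point leaves before randomisation, and the exclusion cannot distort the comparison between arms. For the Part 1 correlations, everyone who completes the session has a score, so the eligible set can be picked out exactly.

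**The planned 32**

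Inputs from section 3: correlation 0.43, power 0.8, alpha 0.05 with sidedness not stated. Fisher's approximation is n = ((z_alpha + z_power) / atanh(r))² + 3.

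- One-sided: n = 32.2. Simulated power of the t-test of r at n = 32 is 0.811, so 32 is reproduced.
- Two-sided: n = 40.1. Simulated power at n = 32 is 0.712.

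The figure of 32 therefore matches a one-sided test and is only a rough benchmark in what follows.

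**How many people could be affected**

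The protocol gives no rate of scores below 18. Let f be the share of Part 1 starters below 18, assumed to be 10%, 20% or 30%.

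If 35 to 40 counts eligible people, the ineligible people who do the recall number N × f / (1 − f):

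| f | N = 35 | N = 40 |
|---|---|---|
| 10% | 3.9 | 4.4 |
| 20% | 8.8 | 10.0 |
| 30% | 15.0 | 17.1 |

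The number of eligible people is then unaffected.

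If 35 to 40 counted everyone who starts Part 1, the eligible people left would be N × (1 − f):

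| f | N = 35 | N = 40 |
|---|---|---|
| 10% | 31.5 | 36.0 |
| 20% | 28.0 | 32.0 |
| 30% | 24.5 | 28.0 |

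The margin over 32 would be gone, before any drop-out, at (35 − 32)/35 = 8.6% to (40 − 32)/40 = 20%. This second reading is strained. Section 3 states the recruitment target in the same section that makes the score a condition of eligibility, and the synopsis lists the number of subjects directly above the inclusion criteria. The natural meaning is 35 to 40 eligible people.

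**The subscale**

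Under Measures, the experiential subscale has nine items scored 0 to 4, so its range is 0 to 9 × 4 = 36. The four expressive items would add up to 4 × 4 = 16, for a whole-scale maximum of 52. The two scores differ, but sections 3 and 4 both name the experiential subscale and the synopsis is an abbreviation of them.

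**The case for a change.** The strongest case for a change is that the text can be made safe for a few lines' work. Care-team identification does not establish a CAINS score, because the protocol assigns the interview to the researcher, and it does not cover the CRIS or poster routes. The criterion concerns current symptoms, so an old rating would not clearly meet it. A protocol that says it keeps burden as low as possible could confirm eligibility before asking for the negative memory.

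The textual part of this stands: no earlier confirmation is described, and no rule for a score below 18 is written. It does not follow that the design must change.

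- The cut-off selects for at least moderate negative symptoms. It is not presented as a safety criterion, and nothing in the protocol suggests that people below it are at greater risk from recall. The cost is one session of unneeded burden for a consenting person who has the section 4 safeguards.
- Putting the CAINS first has its own cost. The interview covers last week's and next week's pleasure and may prime the recall. The person running the task would know the score. A separate earlier session limits the priming but opens a gap between the two measures. Those measures are central to the cross-sectional associations that form the primary objective.
- Every route brings the person into contact with the researcher before taking part. The protocol describes no CAINS at that contact, but does not rule one out.

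**Conclusion.** The concern is right about the order of procedures but does not call for a change. The CAINS comes after the Part 1 recall and before randomisation, so all that is missing for allocation is a written check on a score already available. Applying the stated criterion there, counting only eligible people towards 35 to 40 and using the experiential subscale is what a sensible team would do from the text as it stands. The synopsis wording is a clerical shortening. Keeping the recall first is a fair trade-off between unneeded burden for some people and an unprimed memory measure.

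The size is unknown. Under assumed rates of 10% to 30% below 18, about 4 to 17 people would do the recall before being found ineligible; if screening takes place earlier and is simply not described, the number is near zero. The conclusion rests on the criterion being applied before allocation and on 35 to 40 meaning eligible participants. If people below 18 were in fact randomised or counted, the loss of sample shown above would become real.
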